#### 5.10 Statistical analysis

Both intention to treat and per protocol analysis will be carried out to study the differences in outcome measures between the intervention and control group. Intention to treat analysis is our primary choice of analysis. A minimal treatment with 5 out of 8 darbepoetin injections is defined as acceptable protocol deviation. A p-value < 0.05 will be considered to indicate statistical significance. The number of top-up transfusions per infant and, the number of days of admission for top-up transfusions will be compared between both groups using a Mann-Whitney U test. The time from birth to top-up transfusion will be compared between both groups using survival analysis and a log rank test. The percentage of infants requiring a top-up transfusion up to 2 months of life, the percentage of infants with a high blood pressure and the percentage of infants with high ferritin levels will be compared between both groups using  $\chi^2$  tests. If despite randomization the groups differ at baseline in type of alloimmunization, EPO-levels at birth or treatment with exchange transfusion, a multivariable model may be used in a secondary analysis to correct for these factors.

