#### 4.3 End points

##### *Primary end point:*

- Number of postnatal transfusions per infant from birth up to 3 months of life.

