##### *Secondary end points:*

[figure not shown]
- Number of postnatal transfusions per infant  $\geq 7$  days up to 3 months of life.
- The percentage of infants requiring a postnatal transfusion up to 3 months of life;
- Time from birth to first postnatal transfusion (days);
- Hemoglobin level at first postnatal transfusion (g/dl);
- Number of days of hospitalization and readmission(s) associated with erythrocyte transfusion(s);
- Course of hemoglobin up to 3 months of life.

*Safety end points:*

- The percentage of infants with a systolic blood pressure  $\geq 2$  SD above age adjusted mean systolic blood pressure during treatment;
- The percentage of infants with ferritin levels  $>200$   $\mu\text{g/L}$  during treatment.

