**Figure 1. Hypothesized distribution of number of postnatal transfusions**

## 5. Statistical analyses

### 5.1 Analysis sets

If after randomization parents or caregivers choose to withdraw the infant from participation before day 7, the patient will be replaced and its data excluded from all analyses.

Both intention-to-treat (ITT) and per protocol (PP) analysis will be carried out to study the differences in all outcome measures between the intervention and control group and will be presented. Intention to treat is our primary choice of analysis. The ITT analysis set consists of all randomized patients who did not withdraw before day 7, classified according to allocated treatment regardless of whether they received the assigned treatment and or any protocol deviations. Patients with major protocol deviations will be excluded from the PP analysis set. For patients assigned to the treatment arm, receiving less than 4 out of 8 darbepoetin injections is considered a major protocol violation. Furthermore, in the PP analysis patients will be classified according to treatment assignment.

If the difference between the ITT and PP analysis set is <10%, no per protocol analysis will be performed.

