### 5.2 Analysis of primary and secondary outcomes

The total number of postnatal transfusions per infant from birth to the end of the follow-up period, the number of postnatal transfusions per infant  $\geq 7$  days (which is at the start of intervention in the treatment group) and the number of days of additional admissions for postnatal erythrocyte transfusions will be compared between both groups using a Mann-Whitney U test. The time from birth to first postnatal transfusion will be compared between both groups using a log rank test and will be displayed using Kaplan-Meier survival curves (in this case transfusion-free survival) by treatment group. The period of follow-up in this study is 90 days and as such the end point for included infants that do not receive transfusions during this period, is 90 days in the survival analysis. The percentage of infants requiring a postnatal transfusion up to 3 months of life will be compared between both groups using a  $\chi^2$  test. The average or median number, depending on shape of distribution, of EPO injections in the treatment arm will be reported, as well as a summary of reasons to discontinue EPO treatment.

A multiple linear regression analysis will be performed to correct the association between treatment assignment and the primary outcome (number of postnatal transfusions). The following potential

confounders identified from previous research [unpublished data] are to be corrected for if, despite randomization, there is a baseline difference between the groups: type of alloimmunization, EPO-levels at birth, number of IUTs and treatment with exchange transfusion. In case of a non-normal distribution of the number of postnatal transfusions per neonate, log transformation will be applied. If the assumptions underlying linear regression are violated, or if the value zero occurs often, a Poisson regression will be fitted. If the number of postnatal transfusions per infant <7 days of life shows a difference between the two groups, a sensitivity analysis will be performed by performing the multiple linear regression analysis (or Poisson regression) with and without the transfusions administered <7 days. This will differentiate between the clinical course of early and late anemia and will evaluate more specifically the effect of EPO treatment, which is started at 7 days of age.

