A linear mixed model will be fitted to assess the course of hemoglobin in the treatment and control group which will be graphically depicted. Each infant has repeated weekly hemoglobin measurements as advised in the protocol, but as the frequency of measurements is not mandatory, the data may show missing values at different time points. These missing values are expected to be at random and not completely at random, as it can be anticipated that a measurement is omitted after a previous positive (high) hemoglobin measure which justifies a longer interval between measurements due to the low risk of sudden anemia warranting transfusion. The course of hemoglobin in both groups is expected to have a negative slope after birth due to ongoing hemolysis and a physiological decline of fetal hemoglobin, which will stabilize over the course of several weeks and then show a positive slope as normal physiology recovers or is artificially raised with postnatal transfusions.

To account for the correlation between repeated measurements on the same subject, a random intercept will be included and, if model fit improves, a random slope in the model. The fixed effects will be treatment, time (with a non-linear functional form that will later be determined to match the shape of the expected de- and increase described above) and the interaction treatment\*time. The primary assessment of whether the two groups differ in their hemoglobin course over time will be based on a test on the interaction treatment\*time (a test which will correspond with the most suitable functional form).

[figure not shown]
Throughout the planned analyses, a p-value below 0.05 is regarded as statistically significant. Statistical analysis will be performed using IBM SPSS Statistics 23.0 (Chicago, Illinois, USA).

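### SAP 5.2 lets any planned test with p<0.05 be called statistically significant, including five unadjusted secondary efficacy tests that are not tied to the primary result

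*SAP*

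**What the plan says.** SAP 4.3 names one primary endpoint: "Number of postnatal transfusions per infant from birth up to 3 months of life". It then lists six secondary efficacy endpoints, among them "The percentage of infants requiring a postnatal transfusion up to 3 months of life" and "Course of hemoglobin up to 3 months of life". Two safety endpoints are listed separately.

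SAP 5.2 names a between-arm test for five of the six:

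- Transfusions from day 7 and additional admission days: these, like the primary, "will be compared between both groups using a Mann-Whitney U test".
- Percentage transfused: chi-square test.
- Time to first transfusion: log rank test.
- Hemoglobin course: treatment-by-time interaction in a linear mixed model.

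The sixth, hemoglobin at first transfusion, has no named test, and its standard-care cell in Table 2 holds a dash.

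The section closes with "Throughout the planned analyses, a p-value below 0.05 is regarded as statistically significant". Protocol 5.10 has the same open rule: "A p-value < 0.05 will be considered to indicate statistical significance". SAP 5.1 (Analysis sets) plans both ITT and per-protocol analyses "to study the differences in all outcome measures between the intervention and control group and will be presented", but drops the per-protocol analysis if the two sets differ by less than 10%. The only endpoint labelled exploratory is the 2-year neurodevelopmental outcome in the protocol.

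**The concern.** The sample size is justified for a single two-sided test at 0.05 on the primary. The significance rule, however, gives the same status to every other test. The secondaries are close relatives of the primary: count from day 7, transfused or not, time to first transfusion, days admitted for transfusion. The day-7 count competes with the primary most directly, because it leaves out transfusions given before treatment starts.

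If the primary comparison misses, the written rule still allows one secondary with p<0.05 to be reported as a statistically significant difference. Nothing tells the reader that this was one of several chances. The protocol lists three efficacy secondaries and the SAP lists six, so the set grew without a rule for interpreting it. At stake is what a trial of 44 infants may say about its secondary results; the validity of the primary test is not in question.

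**Working it through.** **1. The plan's own figure.** Inputs from SAP 4.4: 21 per group, difference 1.1, SDs 1.5 and 0.9, two-sided alpha 0.05, stated power 81%.

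- Pooled SD = sqrt((1.5² + 0.9²)/2) = sqrt(1.53) = 1.237.
- Standard error = 1.237 × sqrt(2/21) = 0.382.
- 1.1/0.382 = 2.88, and 2.88 − 1.96 = 0.92, which gives 82.2% power.
- With the usual Mann-Whitney efficiency factor of 0.955, the result is 80.4%.

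Both agree with 81% to within 2 points. The figure covers the primary test only. The documents give no error figure for the secondaries.

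**2. Reference range for five tests.** Take all five null hypotheses as true, each tested two-sided at 0.05. If the tests are independent, P(at least one) = 1 − 0.95⁵ = 22.6%. For equally correlated normal test statistics (400,000 draws, |z| > 1.96):

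| Assumed correlation | 0 | 0.3 | 0.5 | 0.7 | 0.9 |
|---|---|---|---|---|---|
| At least one of five | 22.6% | 21.0% | 18.4% | 14.9% | 10.2% |

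The documents give no correlation, so the whole range of about 10-23% is shown.

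**3. Trial-like simulation, no treatment effect, 22 per arm.** The shape of the transfusion distribution is an assumption, with the mean set to the plan's 1.9.

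- Model A: negative binomial count from day 7 with mean 1.65, and 25% of infants with one transfusion in week 1, so 1.65 + 0.25 = 1.9. Mann-Whitney, chi-square and log rank tests as planned, and a one-degree-of-freedom hemoglobin contrast with correlation 0.3, 0.5 or 0.8 to the count; 6,000 runs for each. At least one of five: 14.8-16.5%.
- Model B: Poisson counts with gamma frailty, early mean 0.3 and late mean 1.6 (total 1.9); 4,000 runs for each setting. At least one of five: 14.8-14.9%, or 13.6% with a continuity-corrected chi-square.

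The rounded summary is 14-16%. It lies in the lower half of the range in step 2 because the transfusion endpoints overlap strongly. In a separate run of Model A at hemoglobin correlation 0.5, the late count and admission days correlated 0.97, and percentage transfused and time to first transfusion 0.90.

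**4. Direction.** The rates above count results favouring either arm. With no effect and equal arms, about half favour darbepoetin.

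- That separate run gave 15.7% two-sided and 7.8% in darbepoetin's favour; a further null simulation gave 14.9% and about 7%.
- The comparator for one two-sided test is 0.05/2 = 2.5%.
- The ratio is therefore between 7/2.5 = 2.8 and 8/2.5 = 3.2.

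**5. The misleading case: primary not significant, at least one of the five significant.** Two-sided, Model A gave 10.7-12.1% and the further simulation 10.6%, so about 11-12%. In darbepoetin's favour, the runs gave 5.2% and 5.5%, so about 5%.

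**The case against.** The strongest reply is that the SAP is not without structure. It states one primary hypothesis, one primary endpoint, separate secondary and safety lists, ITT as the primary analysis, and a sample size built on the primary alone. Reporting unadjusted secondaries behind a single primary is a defensible choice when no claim is reserved for them. All of that stands. What it does not answer is that the SAP goes further than silence: it states that p<0.05 is significant in every planned analysis, and no sentence elsewhere limits this.

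A reader might draw three stronger inferences that the documents do not support:

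- **That the trial's 5% error rate is broken.** It is not. The documents give 0.05 per test and as the primary's alpha. They never promise 5% across the secondaries.
- **That six secondaries are tested, with a rate near 21%.** That needs a test of hemoglobin at first transfusion, which neither document names. It also rests on an assumed correlation of 0.5.
- **That a false claim of benefit arises in 15% or more of null trials.** The two-sided rate includes results favouring standard care. For a benefit claim, the figure is about 7-8%.

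Per-protocol repeats could add a little, but they use nearly the same infants and may be dropped, so they are not counted.

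**Conclusion.** The point holds as a gap in how secondary results may be described. Under the written rule, a null treatment would give at least one significant result among the five named secondary tests about 14-16% of the time, or about 7-8% in darbepoetin's favour. An isolated significant secondary beside a non-significant primary would occur about 11-12% of the time, or about 5% in darbepoetin's favour.

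These sizes assume no effect on any of the five endpoints, two-sided testing throughout, assumed count distributions and a single-contrast hemoglobin test. A hemoglobin interaction test with several degrees of freedom would have no single direction, so the directional figures are approximate. The existence of the gap does not depend on these choices: even at an assumed correlation of 0.9 the rate is about 10%, twice the per-test level. The change is worth making because it is cheap and alters what the trial may conclude.

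**What to change.** In SAP 5.2, replace the blanket significance sentence with:

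> The only confirmatory test is the primary comparison (ITT, two-sided alpha 0.05). All secondary endpoints and all per-protocol analyses are reported with estimates, 95% confidence intervals and nominal p-values, and are not described as statistically significant.

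Add a matching footnote to the p-value column of Table 2, and align protocol 5.10. SAP 4.2 places finalization of the plan before database lock and unblinding, so the change belongs there.

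A fixed sequence that tests the day-7 count second, only if the primary is significant, is an option. It is a preference that the documents do not require.

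The cost is wording only. No data, infants, primary alpha or primary power are affected. The one loss is that an isolated secondary with p<0.05 can no longer be called statistically significant.

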## 5.1 Figures and tables

**Figure 1. Flowchart of study participants**

**Figure 2. Kaplan Meier survival curves for time to first postnatal transfusion by treatment group**

**Figure 3. Hemoglobin course over time by treatment group**

**Table 1. Baseline demographic and clinical characteristics by treatment group**

	EPO treatment (n=22)	Standard care (n=22)
Male - n (%)		
Cesarean delivery - n (%)		
Gestational age at birth - weeks		
Number of IUTs per neonate		
Gestational age at first IUT - weeks		
Hemoglobin level at first IUT - g/dl		
Birth weight - gram		
Hemoglobin level at birth - g/dl		
Reticulocyte count at birth - ‰		
Endogenous erythropoietin at birth - U/L		
Apgar score at 5 minutes		
RhD alloimmunization - n (%)		
Rhc alloimmunization - n (%)		
Kell alloimmunization - n (%)		
Phototherapy - days		
Treatment with exchange transfusions - n (%)		
Maximum bilirubin - mg/dl		

a Value given as mean  $\pm$  SD

b Value given as median (IQR)

**Table 2. Postnatal transfusions and safety measures in EPO treated infants and infants treated according to standard care**

	EPO treatment (n=22)	Standard care (n=22)	p-value
Total number of RBC transfusions per neonate			
Number of RBC transfusions per neonate $\geq 7$ days			
Treatment with postnatal RBC transfusion - n (%)			
Number of days before first transfusion			c
Hemoglobin level at first transfusion - g/dl		-	
Initial hospitalization - days			
Additional hospitalization - days			
Infants with systolic blood pressure $\geq 2$ SD above age adjusted mean during treatment - n (%)		-	
Infants with ferritin levels $>200$ $\mu\text{g/L}$ during treatment - n (%)		-	

a Value given as mean  $\pm$  SD

b Value given as median (IQR)

c Log rank test

